1.0 Background

The prevalence of heart failure with preserved ejection fraction (HFpEF) is comparable to that of heart failure with reduced ejection fraction (HFrEF), carries a similarly grim prognosis [1], and there are no effective disease-modifying medical therapies [2-5]. A common and diagnostic characteristic of HFpEF is dyspnea in response to physiologic stress, such as exercise, that can correlate with increased left-sided filling pressure as measured by invasive hemodynamics [6-7]. While definitive, this modality is not practical to apply widely in clinical practice and remains challenging to pursue even for research studies that aim to evaluate underlying physiologic mechanisms and responses to treatment. Therefore, a non-invasive approach to estimating left-sided filling pressure post-exercise would be helpful in this regard. Standard tissue Doppler imaging on echocardiography (i.e. E/e'), which can be helpful at rest to estimate pulmonary arterial wedge pressure (PAWP) [8], may be less accurate due to fusion of E and A waves at the higher heart rates expected post-exercise.

Prior work using echocardiographic contrast to derive pulmonary transit time (PTT) has suggested that a related metric, pulmonary blood volume (PBV), correlates with PAWP at rest [9-12; IRB #110362, #131075, #131355]. The current study proposes to measure PTT and PBV post-exercise. Demonstration of technical plausibility of this approach would justify future studies to compare directly echocardiographically-derived PBV and invasive exercise hemodynamics post-exercise. If PBV were shown to be a reasonable surrogate for PAWP with exercise, the capability to study the defining feature of HFpEF could be expanded to a non-invasive technique.

2.0 Rationale and Specific Aims

While PTT in patients at rest has been successfully measured via contrast-echocardiography, whether post-exercise data can be reliably obtained and analyzed is unclear. Therefore, we propose to conduct a feasibility study to achieve the following aims:

1. Record the flow of ultrasound contrast across the pulmonary circulation after a standardized exercise protocol
2. Compare PTT and PBV pre- and post-exercise in the same cohort
3. Compare the time from contrast administration to appearance in the right-heart pre- and post-exercise (i.e. vein-to-heart time)
4. Compare PTT obtained by analysis of time-intensity curves to the PTT estimate obtained by visual assessment

3.0 Animal Studies and Previous Human Studies

As above, prior studies have used essentially the same methodology to obtain PTT. The main difference in the proposed study is the addition of post-exercise acquisition of PTT. Ultrasound contrast is commercially available and is widely used in Echocardiography Laboratories worldwide, including at VUMC.

4.0 Inclusion/Exclusion Criteria

To be eligible for enrollment, patients must meet all the following criteria:

Inclusion Criteria:

1. Age \geq 18 years old
2. Able to give informed consent

To be eligible for enrollment, patients cannot meet any of the following criteria:

Exclusion criteria:

1. Known allergic reaction to Definity or Optison ultrasound contrast
2. Pregnancy/Nursing – as assessed/disclosed by the participant
3. Any faculty/staff whose performance will be directly and formally evaluated by the investigator or sub-investigators

5.0 Enrollment/Randomization

As this study is limited in size and aims to evaluate PTT post-exercise, we will concentrate enrollment efforts towards a focused group of prospective participants with (self-reported) adequate exercise capacity. Namely, the focus will be on individuals that attend conferences/meetings given by the Division of Cardiovascular Medicine who report engaging in relatively regular exercise (i.e. some form of aerobic exercise at least twice per month). This group includes faculty, sonographers, administrators, support staff, and occasional guests from other departments (particularly for inter-disciplinary conferences). Within this pool of potential candidates, there is sufficient demographic diversity to permit inclusion of individuals across a range of age, gender, and ethnicity. Cardiology fellows and NPs are not eligible to avoid the appearance of undue influence to participate.

Invitations to participate in the study will be made to those in attendance at divisional conferences (i.e. Faculty Meeting, Echocardiography conference) and will not target specific individuals within the above groups. Interested individuals will contact KSP, who will then help facilitate the study visit at the CRC.

6.0 Study Procedures

All study procedures will take place over a single day during a single visit to the CRC. Participants will experience the following:

1. **Baseline demographics and anthropomorphic measurements.** Basic information on age, gender, and self-identified ethnicity will be collected along with height and weight.
2. **Pre-exercise echocardiographic evaluation.** This assessment will be performed by the CRC sonographer and will include heart rate, LVOT diameter, LVOT VTI, mitral valve inflow, mitral valve tissue Doppler imaging, IVC size/respirophasic changes in caliber, and a recording of the apical 4-chamber

- view (the view in which contrast flow will be recorded) to ensure adequate visualization.
3. **Pre-exercise PTT measurement.** Following placement of a standard peripheral IV by a CRC nurse, ultrasound contrast will be administered and the pathway of the contrast from entry into the right-heart through appearance in the left-heart will be recorded in order to obtain the data necessary to measure PTT. The interval between the beginning of the contrast injection and the appearance in the right-heart will be recorded. The IV line will then be flushed with saline to remove any residual contrast. After the acquisition of these data, the 'FLASH' feature of the ultrasound machine will be employed to rapidly remove the remaining contrast from the field of view such that there is minimal, if any, residual contrast when it is time for administration of contrast post-exercise.
 4. **Exercise protocol.** Participants will exercise on a treadmill (provided by the Metabolic Core) following a Standard Bruce Protocol until their heart rate reaches ~ 2.5-times their baseline level or until they reach maximum effort. Exercise capacity, blood pressure, and heart rate will be recorded at standard intervals throughout exercise. If it proves to be more logically favorable, an exercise bicycle (also supplied by the Metabolic Core) can be used rather than a treadmill.
 5. **Post-exercise PTT measurement.** This administration of contrast will be similar to the pre-exercise PTT measurement and will occur as soon as an adequate echocardiographic image can be obtained following exercise. Heart rate will also be recorded during this step. Mitral valve inflow, mitral valve tissue Doppler imaging, and IVC size/respirophasic changes in caliber will be re-assessed as well.
 6. **Contingencies for additional contrast administration.** Should there be unforeseen technical issues with contrast administration or image acquisition at pre- or post-exercise, additional doses of contrast can be given as permitted by the remaining volume in the vial (typically, 1-2 mL of contrast are used per injection and a single vial yields 8-10 mL of contrast).

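### The eligibility rules contain no exclusion for known cardiac disease or exertional symptoms, and no described step screens for them before an exercise test that may run to maximum effort

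*Combined protocol and SAP*

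**What the plan says.** All references are to the combined protocol and SAP.

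- **Section 4.0** has two inclusion criteria: adulthood and capacity to consent. Its exclusions open with "To be eligible for enrollment, patients cannot meet any of the following criteria" and number three: contrast allergy, pregnancy or nursing, and staff whom the investigators formally evaluate. Pregnancy and nursing are established "as assessed/disclosed by the participant".
- **Section 5.0** directs recruitment towards "prospective participants with (self-reported) adequate exercise capacity", meaning people "who report engaging in relatively regular exercise (i.e. some form of aerobic exercise at least twice per month". It anticipates "inclusion of individuals across a range of age, gender, and ethnicity". It adds one further bar: "Cardiology fellows and NPs are not eligible to avoid the appearance of undue influence to participate".
- **Section 6.0** collects demographics, height and weight in step 1. In step 2 a sonographer makes resting echocardiographic measurements and records the apical four-chamber view, "the view in which contrast flow will be recorded) to ensure adequate visualization". Step 4 is the exercise test, which continues "until their heart rate reaches ~ 2.5-times their baseline level or until they reach maximum effort".
- **Section 7.0** lists acute coronary syndrome and arrhythmia among the risks of exercise and expects them to be small in the target population.
- **Section 11.0** keeps study staff out of participants' medical records, apart from documenting participation and consent.

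**The concern.** Section 7.0 identifies three risk-bearing procedures: the IV line, the contrast agent and the exercise. Section 4.0 has exclusions suited to the contrast agent (allergy, pregnancy or nursing) but none suited to the exercise, although the plan itself names cardiac events as an exercise risk. Applied exactly as written, the rules admit a volunteer with known coronary disease or a known arrhythmia to a test that may end at maximum effort.

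What is at stake is participant protection. Recording heart rate and blood pressure during the test may help to limit the consequences of an event. It cannot identify beforehand a person who should not start.

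**Working it through.** The plan gives no figure to reproduce here, and no sample-size or error-rate formula applies. The check is to follow a hypothetical volunteer with known, asymptomatic coronary disease who exercises a few times a month through each point where the plan could stop them.

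1. **Inclusion, Section 4.0.** Adult and able to consent. The volunteer passes. There is no upper age limit, and Section 5.0 expects a range of ages.
2. **Exclusion, Section 4.0.** Contrast allergy, pregnancy or nursing, reporting line. None applies.
3. **Ineligibility rule, Section 5.0.** The bar on cardiology fellows and NPs is there to avoid undue influence and has nothing to do with health.
4. **Recruitment focus, Section 5.0.** This is the nearest thing to a fitness screen. It is worded as where enrollment effort is concentrated and does not appear among the Section 4.0 criteria. It rests on self-report. Adequate exercise capacity does bear on exertional limitation, so a person limited by symptoms may not put themselves forward. It does not bear on disease without symptoms, so this volunteer passes.
5. **Step 1, Section 6.0.** No medical history, medication or symptom item is listed.
6. **Step 2, Section 6.0.** The resting echocardiogram comes before exercise and could reveal an abnormality. Its stated uses are measurement and image adequacy, and no finding is tied to withholding exercise.
7. **Chart review, Section 11.0.** Not permitted for this purpose. That is reasonable when participants are likely to be colleagues, but it means the information has to come from the participant.
8. **Step 4, Section 6.0.** The test starts. The heart-rate limit may end it early in some people, but maximum effort is the stated alternative endpoint.

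No described step stops this volunteer. A table of target heart rates would add nothing: it would need assumed resting and peak rates that the documents do not give, and it would show only that the test can be strenuous, which the maximum-effort endpoint already says.

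The contrast-allergy and pregnancy exclusions imply that some health questions are asked somewhere, although step 1 does not list them. Cardiac questions might be asked at the same time. Even so, Section 4.0 would give staff no criterion for declining a person who answered yes.

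**The case against.** The best case on the other side has four parts.

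**Screening may exist elsewhere.** The text reviewed omits consent pages, and these could carry an instruction to report heart disease or chest pain. Local exercise-laboratory practice is not described either. This stands as a limit. A reader might infer that nobody is screened in practice, and the documents do not support that. The point is confined to the eligibility rules and procedures in the text reviewed.

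**Section 7.0 claims only that the risk is small.** A reader might take that section to presume that nobody with cardiac disease takes part. It does not say so, and a small risk is compatible with an occasional participant who has disease. This also stands. What remains is that the reassurance refers to a target population that the eligibility rules do not secure.

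**The recruitment focus does some work.** It does: people limited by exertional symptoms are less likely to report adequate capacity. It is much weaker against known disease without symptoms, and Section 4.0 does not enforce it.

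**The pool is medically informed.** It includes faculty and sonographers, but also administrators, support staff and occasional guests. The plan writes down contrast allergy and pregnancy even though volunteers would know of these themselves, so self-knowledge has not been treated as a substitute for a criterion.

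**Conclusion.** The point holds for the text reviewed. Section 4.0 lacks an exclusion for known cardiac disease or exertional symptoms, and no described step screens for either before the exercise test. It should be corrected on participant-protection grounds.

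Its size is limited and cannot be quantified from the documents. It might be tempting to say that the gap exposes all 15 planned participants. It does not: it matters only for volunteers who have such disease or symptoms, and that number is unknown and possibly zero. No event rate can be derived. Nor is the analysis put in doubt, because the Wilcoxon signed-rank comparison of pre- and post-exercise values is unaffected.

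The conclusion assumes that the omitted consent pages contain no operative cardiac exclusion. If they do contain one, the remaining task is to carry it into Section 4.0.

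**What to change.** 1. Add one exclusion to Section 4.0, as disclosed by the participant, which is the mechanism already used for pregnancy and nursing. It should cover known coronary disease, clinically significant arrhythmia or other significant cardiac disease, and exertional chest pain, syncope or undue breathlessness.
2. In Section 6.0, ask about these by short self-report before IV placement. A positive answer means that the volunteer does not exercise unless the PI or a qualified delegate clears them. The text assigns no physician to the visit, so the protocol should name the role that makes this decision.

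The Section 11.0 limit on chart access, the target of 15 and the analysis can all stay as they are.

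**Cost.** One protocol line, a short form and a named decision-maker. A few volunteers may be declined and replaced. Colleagues would disclose limited health information to the study team, which is a real cost given the relationship that Section 11.0 is written to protect, so the questions should be kept few. Self-report will not find undiagnosed disease. The change addresses what participants already know.

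### Post-exercise pulmonary blood volume is part of the primary analysis, but step 5 lists no LVOT VTI and the plan neither defines PBV nor names another post-exercise stroke-volume source

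*Combined protocol and SAP*

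**What the plan says.** Post-exercise PBV is promised three times: in Section 1.0 (Background), in Aim 2 of Section 2.0, and in Section 10.0, where the primary analysis is a within-person comparison of PTT and PBV before and after exercise by the Wilcoxon signed rank test. Section 1.0 describes PBV only as a measure related to PTT, citing earlier work; no formula follows there or elsewhere.

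Section 6.0 sets out the measurements. The resting evaluation (step 2) "will include heart rate, LVOT diameter, LVOT VTI, mitral valve inflow, mitral valve tissue Doppler imaging", followed by IVC assessment and an apical four-chamber recording. In step 3 the passage of contrast "will be recorded in order to obtain the data necessary to measure PTT". For the post-exercise study, step 5 says: "This administration of contrast will be similar to the pre-exercise PTT measurement". It adds "Heart rate will also be recorded during this step" and then "Mitral valve inflow, mitral valve tissue Doppler imaging, and IVC size/respirophasic changes in caliber will be re-assessed as well". On timing, the section opens with "All study procedures will take place over a single day during a single visit to the CRC".

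**The concern.** The protocol takes LVOT diameter, LVOT VTI and heart rate at rest, which are the usual ingredients of a Doppler flow estimate. After exercise it repeats the heart rate and drops both LVOT items, although PBV is to be compared across the two time points. A sonographer working from step 5 as written has no instruction to record LVOT VTI, and after a single visit the trace cannot be recovered.

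At stake is the PBV half of the primary comparison. The analyst could be left to choose, with the data already in hand, between missing values, a resting stroke volume carried forward, and a method the plan does not mention. PBV is also the quantity that Section 1.0 puts forward as a possible non-invasive surrogate for wedge pressure, so it is not a side measurement.

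**Working it through.** There is no stated figure to reproduce: the target of 15 participants has no power calculation behind it, and this point disputes no number in the plan.

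**1. The two lists in Section 6.0, side by side**

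| Item | Before exercise (step 2) | After exercise (step 5) |
|---|---|---|
| Heart rate | listed | listed |
| LVOT diameter | listed | not listed |
| LVOT VTI | listed | not listed |
| Mitral inflow | listed | listed |
| Mitral tissue Doppler | listed | listed |
| IVC | listed | listed |

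Four of the six measurements return after exercise. The two that do not are the LVOT items. The resting diameter could be reused, so the VTI is the main gap.

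**2. Could another sentence supply the missing item?**

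- The similarity clause in step 5 has the contrast administration as its subject and refers back to the PTT measurement in step 3. Step 3 contains no LVOT item; those are in step 2.
- Section 3.0 says that "prior studies have used essentially the same methodology to obtain PTT". That carries a method over for PTT and does not mention PBV.
- Section 1.0 links PBV to cited work and prior protocols. Those may define it, but a formula found there would not put a measurement into step 5.
- Mitral inflow or the apical four-chamber view could conceivably yield a flow estimate. The plan names neither for that purpose.

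**3. Size of the error if resting stroke volume is carried forward**

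Assumption, not stated in the documents: PBV = SV x (HR/60) x PTT, with SV = LVOT area x LVOT VTI. Let r = SV after exercise / SV at rest. Using resting SV with post-exercise HR and PTT, the HR and PTT terms cancel:

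relative error = SV_rest / SV_post - 1 = 1/r - 1

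| r (assumed) | 1/r | error in post-exercise PBV |
|---|---|---|
| 0.9 | 1.111 | +11.1% |
| 1.0 | 1.000 | 0% |
| 1.1 | 0.909 | -9.1% |
| 1.2 | 0.833 | -16.7% |
| 1.3 | 0.769 | -23.1% |
| 1.4 | 0.714 | -28.6% |

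The documents give no value for r, so the range runs to both sides of 1.

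**4. What that can do to the paired comparison**

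Step 4 has participants exercise "until their heart rate reaches ~ 2.5-times their baseline level or until they reach maximum effort". Take the 2.5-fold target as the heart-rate ratio, for illustration only, since some may stop at maximum effort and the rate may have fallen by the time of imaging. With t the post/pre PTT ratio (assumed), the apparent PBV ratio is 2.5 x t and the actual ratio is 2.5 x t x r.

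- t = 0.4: apparent 2.5 x 0.4 = 1.00, so no change. Actual: 0.90 at r = 0.9, 1.20 at r = 1.2, 1.40 at r = 1.4. A change is hidden.
- t = 0.3: apparent 2.5 x 0.3 = 0.75, a fall of 25%. Actual at r = 1.4: 0.75 x 1.4 = 1.05, a rise of 5%. The direction is reversed.

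If r lies on the same side of 1 in most participants, this is a systematic error, and more pairs would not average it out.

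**The case against.** The strongest reply is that this is probably a drafting omission. Step 5 does not say that only the listed items are taken, an experienced sonographer may record LVOT VTI anyway, and the cited earlier work may already fix both the formula and the acquisition. That is possible, and nothing in the documents shows a deliberate decision to leave the item out. It does not remove the gap, because the protocol is the text the sonographer and the analyst work from.

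A second reply is that everything about PBV beyond the omission depends on a formula the documents do not state. This stands. It is why the effect on the PBV endpoint is given as conditional.

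A third concerns a stronger reading. A reader might infer that, with step 5 followed as listed, post-exercise PBV could not be calculated in any of the 15 participants. The documents do not support that. Resting LVOT diameter and VTI are collected, post-exercise heart rate and PTT are collected, and together they yield a number. The plan neither proposes nor forbids that substitution. What is missing is a measured post-exercise stroke volume, and the number obtained without it may be biased.

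Finally, this is a feasibility study with no power calculation, which limits how much weight one secondary-looking omission deserves. That argues for a modest grading rather than for dismissal, since PBV is named in the primary analysis.

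**Conclusion.** The point holds as a cheap improvement. Confidence is high that step 5 does not list LVOT VTI, that PBV is not defined, and that no other post-exercise stroke-volume source is named. The consequence for the PBV endpoint is conditional on PBV being transit time multiplied by LVOT-derived flow. On that assumption, any post-exercise PBV under step 5 as listed would be missing, would rest on resting stroke volume, or would come from a method chosen outside the plan. For the second of these, the error runs from +11% to -29% over an assumed stroke-volume ratio of 0.9 to 1.4, enough to hide or reverse a change.

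It would be wrong to conclude that the primary analysis fails as a whole: PTT, vein-to-heart time and the Bland-Altman comparison of the two PTT techniques do not use stroke volume and are unaffected.

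**What to change.** - Add LVOT VTI to the step 5 list, recorded after the contrast transit so that the injection is not delayed. Note the heart rate at transit and again at the VTI recording. The resting LVOT diameter can be reused.
- State in the protocol the PBV formula the study will use. The sponsor should supply its own; the expression used in the check above is only an assumption.
- If another stroke-volume source is intended, name it and use it both before and after exercise.
- State that resting stroke volume will not replace a missing post-exercise value in the primary PBV comparison, and report how many participants have an analysable post-exercise PBV.

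Cost: one extra Doppler trace in an echo session that already takes place, slightly longer scanning, and a short protocol edit. The remaining weakness is that the VTI will not be exactly simultaneous with contrast transit while the participant is recovering; the two heart-rate readings give some indication of how much has changed in between.

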7.0 Risks

The key study procedures that could incur risk include placement of a peripheral IV, administration of echocardiographic contrast, and treadmill/stationary bicycle exercise.

The risks associated with peripheral IV placement include damage to the vein, inadvertent arterial puncture, infection, and infiltration into the underlying skin. In general, and in this setting in particular (i.e. non-acute ill individuals having an IV placed by an experienced nurse), complications of peripheral IV placement are rare.

The safety record of Definity and Optison ultrasound contrast, the two agents approved for clinical use in the United States, is long-established and has been presented in prior protocols cited above. In summary, studies reporting on hundreds of thousands of administered doses have shown extremely low adverse event rates.

Specifically, with Definity, serious cardiopulmonary reactions (including fatalities) have occurred during or following administration; most serious reactions occur within 30

minutes of administration. These include: Cardiovascular: Flushing (1%) Central nervous system: Headache (2%) Gastrointestinal: Nausea (1%) Neuromuscular & skeletal: Back pain (1%) Renal: Renal pain (1%).

Specifically, with Optison, serious cardiopulmonary reactions (some fatal) have occurred uncommonly during or within 30 minutes following administration. Serious anaphylactoid reaction. Cardiovascular: Flushing (4%), chest pain (1%) Central nervous system: Headache (5%), dizziness (3%), chills ($\leq 1\%$), fatigue ($\leq 1\%$), malaise ($\leq 1\%$) Gastrointestinal: Nausea ($\leq 4\%$), vomiting ($\leq 4\%$), dysgeusia (2%) Local: Discomfort at injection site (1%) Neuromuscular & skeletal: Weakness ($\leq 1\%$) Respiratory: Dyspnea (1%), flu-like symptoms (1%) Miscellaneous: Fever ($\leq 1\%$).

The risks associated with exercise on the treadmill (Standard Bruce Protocol) or exercise bicycle include mechanical injury (from loss of balance or equipment failure), muscle/joint pain, orthopedic injury, and unanticipated cardiac events (i.e. triggering of acute coronary syndrome or arrhythmias). In the population targeted for this study, these risks are anticipated to be small.

8.0 Reporting of Adverse Events or Unanticipated Problems involving Risk to Participants or Others

Adverse events determined to be related to the study will be reported to the VUMC IRB by either the PI or KSP as required by VHRPP policy III.L within 7 calendar days of the PI's knowledge of the problem.

